**Are you currently taking any medications for memory loss or dementia?**

Yes (1)  No (0)

**\*If yes, please indicate which one(s) (check all that apply):**

donepezil (Aricept)       galantamine (Razadyne)  rivastigmine (Exelon)  
 memantine (Namenda)       other \_\_\_\_\_

**Have you been on a steady dose for the past 3 months?**

Yes (1)  No (0)      If NO 

**Are any changes to these medications planned in the next 6 months?**

Yes (1)  No (0)      If NO 

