## APPENDIX B.

### SleepTIGHT phone screening script

#### INTERVIEWER INSTRUCTIONS

Read **bolded** text verbatim. Answer any questions as needed. Record all contacts in the contact log.

If a  is reached at any point, say: **I'm sorry, but unfortunately you are not eligible to participate in this study.** [Explain why they are not eligible if appropriate and indicate reason for ineligibility].

- Not fluent in English
- No diagnosis
- No device to access content
- Age < 18
- Medical condition
- Vision/hearing impairment
- Psychiatric condition
- Moderate/severe
- Low QDRS
- No study partner
- Research study
- Dementia medication change
- Other \_\_\_\_\_

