## ELIGIBILITY CRITERIA

**Are you able to speak and understand English?**

Yes (1)  No (0)

If NO 

**\*\* Do you have a diagnosis related to memory loss?**  Alzheimer's disease (1)

Vascular dementia (2)  Dementia unspecified (3)  Mixed dementia (4)

Mild cognitive impairment (5)

Not sure, but could ask doctor (6)  Other (7) \_\_\_\_\_

**Do you have history of brain tumor or significant head trauma (including for instance, loss of consciousness >30 minutes?)**

Yes (1)  No (0)

If YES 

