**Has a doctor ever diagnosed you with brain infarction?**

Yes (1)  No (0)

If YES 

**Has a doctor ever diagnosed you with any severe psychiatric disorders in the past 2 years such as depression, bipolar disorder, schizophrenia or any others?**

Yes (1)  No (0)

If YES 

Specify which: \_\_\_\_\_

**Has a doctor ever diagnosed you with any major neurological disease such as Parkinsons' multiple sclerosis, epilepsy, or Huntington's disease?**

Yes (1)  No (0)

If YES 

Specify which: \_\_\_\_\_

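### In the phone screener, the item on planned dementia-medication changes branches on 'No', against the direction of every other yes/no eligibility branch

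*Protocol*

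**What the plan says.** Appendix B of the Protocol is the telephone script that decides who goes on to further screening. Its Interviewer Instructions say that when a symbol is reached the caller is told that "unfortunately you are not eligible to participate in this study", and that the interviewer should "indicate reason for ineligibility". A list of reasons follows; one of them is "Dementia medication change".

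The eligibility section then has a short block on dementia drugs:

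- It opens with "Are you currently taking any medications for memory loss or dementia", followed by a list of drugs to tick if the answer is yes.
- The next item asks whether the dose has been steady for three months. Its branch is printed on 'No'.
- The next asks "Are any changes to these medications planned in the next 6 months". Its branch is also printed on 'No'.

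The Protocol's inclusion and exclusion criteria contain no rule on stable dosing of dementia drugs or on planned changes to them. Exclusion 6 speaks generally of confounding concomitant treatment and names psychotropic and hypnotic drugs. The SAP (Follow-up and outcome measures) says that eligibility rates will be assessed, under a primary goal of feasibility.

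**The concern.** The two consecutive drug items share one answer line but run in opposite directions. A 'No' to the steady-dose item signals instability; a 'No' to the planned-change item signals stability. If the branch means a stop in both places, the script turns away callers whose treatment is stable and expected to stay so, and keeps those whose treatment is about to change.

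This is an operative instruction, since the interviewer acts on it during the call. The trial is a 40-person pilot whose primary outcomes are feasibility measures, so who is screened out, and why, is part of what it sets out to learn.

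**Working it through.** The plan gives no figure to reproduce here. The check compares each printed branch with the answer that would count against the caller.

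**Step 1. What the branch does.** The symbol is not visible in the text available for this review, and that is not a fault of the plan. The stop is inferred from the Interviewer Instructions, which make reaching the symbol an ineligibility stop, and from the layout, because the same 'If YES' or 'If NO' followed by a gap appears throughout the section.

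**Step 2. Direction of each yes/no branch in the eligibility section.**

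| Item | Branch printed on | Unfavourable answer | Protocol criterion |
|---|---|---|---|
| English | No | No | Inclusion 5 |
| Brain tumour or head trauma | Yes | Yes | Exclusion 2 |
| Brain infarction | Yes | Yes | Exclusion 3 |
| Psychiatric disorder | Yes | Yes | Exclusion 4 |
| Neurological disease | Yes | Yes | Exclusion 1 |
| Sleep disorder | Yes | Yes, if inadequately treated | Exclusion 9 |
| Steady dose, 3 months | No | No | None stated |
| **Planned change, 6 months** | **No** | **Yes** | **None stated** |
| Psychotropic or hypnotic drugs | Yes | Yes | Exclusion 6 |
| Alcohol or substance abuse | Yes | Yes | Exclusion 7 |
| Shift work | Yes | Yes | Exclusion 8 |

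For example, "Are you able to speak and understand English" branches on 'No' and "Has a doctor ever diagnosed you with brain infarction" branches on 'Yes', each the unfavourable side. For the two drug items the unfavourable answer is taken from the sense of the questions and from the reason "Dementia medication change", because no criterion covers them. The table has 11 rows: 10 match and 1 does not. Leaving out the sleep-disorder item, which also asks about treatment, gives 10 rows with the same single exception. The finding does not depend on the count.

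**Step 3. Who reaches the item.** On the stop reading, a drug user without a steady dose has already been stopped one item earlier. Two kinds of caller remain:

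- steady dose, no change planned: stopped;
- steady dose, change planned: continues.

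That the item is put only to drug users is itself inferred, from its wording and from the conditional drug list before it. No skip instruction is printed.

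**Step 4. If the symbol is not a stop.** The item then prints no stop for a planned change either. That is consistent only if planned changes were never meant to exclude anyone.

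**Step 5. What happens next.** A caller who passes the whole script is told that they may proceed, and later has a Zoom interview covering medical history (SAP, Baseline screening/Randomization), where a planned change may come to light. For a caller stopped here, the script prints no further step.

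**The case against.** The strongest reply is that this is probably an answer line carried over from the item above, in an appendix, affecting a subgroup that may be very small. Exclusion 1 removes people with a diagnosis of Alzheimer's disease or other dementia, and they are the likeliest users of these drugs. Interviewers are told to explain the reason for ineligibility where appropriate, and having to say that someone is excluded because no change is planned would tend to expose the slip. Randomisation, outcome measures and the analysis models are untouched. All of this stands, and it holds the point at minor level. It does not remove it: the script names these drugs, and the SAP plans to study people with MCI or mild Alzheimer's disease, so such callers are foreseen.

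Four stronger readings are tempting, and the documents do not support them:

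- *The script breaches a stated eligibility criterion.* The criteria contain no stability or planned-change rule to breach. The reason "Dementia medication change" does not settle the matter, because the steady-dose item alone could account for it.
- *Wrongly stopped callers would be hidden under the reason 'Other'.* The list ties no reason to any item. An interviewer could as easily tick the medication-change reason.
- *The eligibility rate is distorted by a known amount.* The SAP does not define that rate, and the share of callers on these drugs is not given.
- *People have been wrongly turned away.* Nothing in the documents shows that anyone was screened this way.

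**Conclusion.** The point holds as an internal inconsistency in the screening script, at the level of a minor correction. The printed branch on the planned-change item faces the opposite way from the steady-dose item, from the other yes/no branches in the section, and from the natural sense of the listed reason about medication change.

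That the consequence is a stop rests on the Interviewer Instructions and the shared layout; a look at the symbol on the original page would confirm or remove that assumption. If it is a stop, the callers affected are dementia-drug users on a steady dose: those with no planned change are lost, and those with one continue. Their number cannot be derived and may be small. The two outcomes are not symmetric, because a caller who is passed still meets a later eligibility interview and a caller who is stopped does not. The documents do not settle which rule was intended.

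**What to change.** Reconcile the planned-change item with the steady-dose item, with the Interviewer Instructions and their list of reasons, and with the Protocol's inclusion and exclusion criteria. The study team should:

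1. confirm what rule, if any, is intended for planned changes to dementia drugs;
2. correct the printed branch to match it;
3. say whether the medication-change reason covers planned as well as past changes;
4. add the rule to the eligibility criteria if it is kept.

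If screening has begun, check the contact log for every caller stopped or passed at this item, whatever reason was recorded.

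The cost is a one-line script edit, at most one line in the criteria, and a log check if calls have been made. There is no added burden on participants.

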**Have you been on any psychotropic or hypnotic medications within the past 30 days?**

No (0)       Yes (1) If YES 

please describe: \_\_\_\_\_.

**Do you have a history of alcohol or substance abuse within the past 2 years?**

No (0)       Yes (1) If YES 

**Are you employed as a shift-worker?**

No (0)       Yes (1) If YES 

**Do have vision or hearing impairment that could affect your ability to participate?**

No (0)       Yes (1)      If Yes, please describe: \_\_\_\_\_.

**The next questions will ask about what devices you could use for the online material and assessments.**

**Do you have access to a device with a video camera that can connect to the internet? For example, an iPad, iPhone or other mobile device? *Ineligible if they do not have a mobile device or tablet - our platform will only support those devices.***

Yes (1)       No (0) If UNSURE, gather more information and continue.

other (specify type: \_\_\_\_\_) Explain that camera access is only needed at certain times for cognitive testing and follow-up measures. Otherwise only a smartphone is needed.

**Are you willing to participate in the SleepTIGHT material for about 35 minutes on a weekly basis over six weeks?**

Yes (1)       No (0) 

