### Feasibility

Proportion of eligible participants consented

- Proportion of participants randomized after baseline assessment
- Number of CBT-I sessions completed
- Adherence/compliance rates
- Follow-up rates
- Missing data (data completeness)
- Time needed to collect and analyze data

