**Are you currently participating in another research study?**

No (0)       Yes (1) If Yes, please describe: \_\_\_\_\_.

**Great, it looks like so far you are eligible to proceed – though we will need to do a few more tests to decide if you are eligible for the participation in the study. The next step is to conduct a screening for insomnia, and we will get back to you with your final eligibility.**

Subject's Initials

ID#

Date

Time

AM/PM

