3 Follow-up and outcome measures. The primary goal of this research is to pilot test the feasibility of implementing this CBT-I program in patients with MCI or mild AD. Following the last session of CBT-I, participants will be asked to report their satisfaction and acceptability of the treatment. We will also assess eligibility, consent, and retention rates, as well as data quality and completeness. To explore the initial effects of this treatment on sleep and cognition, we will repeat baseline measurements, including the neuropsychological battery and the questionnaires (ISI, PSQI, ESS and SF-36) towards the end of the intervention.

STATISTICAL ANALYSES

To assess the randomization, baseline demographic and clinical characteristics will be compared between arms using parametric (e.g. t-test) or nonparametric test (e.g. chi-square, Wilcoxon tests); variables that are not balanced across treatment arms will be adjusted for in subsequent analyses. The primary analysis will use the intent-to-treat principle. Secondary subgroup analyses will assess the role of treatment adherence on outcomes, using measures of compliance applicable to both study arms, thus avoiding the well-known biases of a “compliers only” analysis.

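### The phone script screens the caller's own willingness as an eligibility item and has no code for refusal, which can raise the primary consent proportion when screening precedes consent

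*Protocol*

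**What the plan says.** - **The item.** Protocol Appendix B asks "Are you willing to participate in the SleepTIGHT material for about 35 minutes on a weekly basis over six weeks", with Yes and No as answers. It is the second-last item under the heading "ELIGIBILITY CRITERIA", and no new heading comes between. Only afterwards does the interviewer say "Great, it looks like so far you are eligible to proceed".
- **The formal criteria.** The row on diagnosis and main inclusion criteria in the protocol synopsis requires a willing study partner. It does not list the participant's own willingness to do the weekly material.
- **The exit.** Under Interviewer Instructions, reaching a stop mark means saying "I'm sorry, but unfortunately you are not eligible to participate in this study" and indicating the reason. The list has 12 named reasons, for example "Dementia medication change", plus Other. None is a refusal.
- **The outcome.** The first item under Primary Outcomes, Feasibility is "Proportion of eligible participants consented". The SAP adds only "We will also assess eligibility, consent, and retention rates, as well as data quality and completeness". Neither document defines who counts as eligible, or when.
- **The order of steps.** The protocol section on initial contact and screening has the consent form signed before the Insomnia Severity Index (ISI). The SAP's section on baseline screening and randomization has eligibility determined after consent. Appendix A's study overview puts screening before the paperwork, and Appendix B prints the consent review after the screening items and the ISI.

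**The concern.** A caller who meets every listed criterion but will not take on the weekly workload has refused; that person is not ineligible. A consent proportion among eligible people exists to count such refusals. If the script sends this caller out as ineligible, and nothing in the record separates refusal from ineligibility, the caller drops out of any denominator built from the script. The proportion then describes uptake among people who have already agreed to the workload. Leaving refusers out can only raise it.

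In a pilot whose primary purpose is feasibility, this rate feeds directly into recruitment planning for a larger trial. An overstated rate means too few people approached and too short a recruitment period.

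**Working it through.** The documents state no consent rate, target or recruitment calculation, only a planned 40 subjects, so there is no figure to reproduce. The check has four steps.

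**1. Does a No trigger the exit?** The stop symbol is lost in the extracted text, so compare the items. Those on English, head trauma, psychiatric disorder, psychotropic medication, substance abuse and shift work show a blank where a symbol would follow the disqualifying answer. The willingness item shows the same blank after No. The items on diagnosed cognitive impairment, memory medication, vision or hearing, and other research studies do not. A stop is very probable. The printed form would settle it.

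**2. Size when the script precedes consent.** Let C = number consented, E = number counted as eligible by the script, and D = number otherwise eligible who say No.

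- Rate by script = C/E
- Rate with decliners restored = C/(E + D)
- Ratio = (E + D)/E = 1 + D/E = 1/(1 − w), with w = D/(E + D)

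For an assumed rate of 50% with decliners restored:

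- w = 10%: 0.50/0.90 = 55.6%
- w = 20%: 0.50/0.80 = 62.5%
- w = 30%: 0.50/0.70 = 71.4%

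In counts, assume C = 40 (the planned sample) and E = 50. The script rate is 40/50 = 80.0% (95% Wilson interval 67.0 to 88.8).

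| D (assumed) | w = D/(50 + D) | 40/(50 + D) | Factor 1 + D/50 |
|---|---|---|---|
| 0 | 0% | 80.0% | 1.00 |
| 3 | 5.7% | 75.5% | 1.06 |
| 6 | 10.7% | 71.4% | 1.12 |
| 12 | 19.4% | 64.5% (52.1 to 75.3) | 1.24 |
| 33 | 39.8% | 48.2% | 1.66 |

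The gap depends on E. With about 20% declining and C = 40, it is 20.0 percentage points at E = 40, 15.5 at E = 50, 13.3 at E = 60 and 10.0 at E = 80.

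**3. Not every decliner would have proved eligible.** As printed, the willingness item comes before the ISI and the Quick Dementia Rating System (QDRS). If E is counted after those screens and only a fraction f of those who say No would have passed them, the comparable rate is C/(E + fD). With C = 40, E = 50 and 12 saying No:

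- f = 1: 40/62 = 64.5%
- f = 0.5: 40/56 = 71.4%
- f = 0: 40/50 = 80.0%

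Restoring everyone therefore gives an upper bound on the distortion.

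**4. Size when consent precedes eligibility.** Under the protocol's contact section and the SAP, everyone found eligible has already consented. C and E then coincide and C/E is near 100% by construction, whatever the willingness item does. The formula in step 2 does not apply.

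**The case against.** The strongest reply is that the documents do not show the bias occurring.

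- **The stop mark is inferred.** This stands. The text pattern is also imperfect: vision or hearing impairment and other research participation are listed reasons for ineligibility, although their items show no stop. But telling someone who has just refused the programme that they may proceed would make little sense.
- **No denominator is defined.** This stands. Staff log all contacts and could write a refusal under Other, then add it back. A reader might infer that the reported rate is inflated as a matter of fact. The documents support only that it can be, because nothing equates eligible with having passed the script. Yet the list offers no code that would make adding back reliable.
- **The order matters.** This stands. A reader might infer that the problem holds whichever way consent and screening are ordered. Step 4 shows that it does not. Even Appendix B is mixed: its consent review is printed after the screening items but ends by offering to screen the caller.
- **Refusals can occur earlier.** Appendix A describes the sessions and asks about interest before any eligibility item, so few may be left to refuse later. This limits the likely size. The workload described there (about an hour per session) differs from the 35 minutes in Appendix B, so an early yes does not settle the later answer.
- **Acceptability.** A reader might infer that refusal over burden also vanishes from the acceptability outcome. The SAP collects satisfaction and acceptability after the last session, and nothing shows that outcome was meant to cover callers who never enrolled.
- **Weight.** The consent proportion is one of seven feasibility items, and no target or test depends on it.

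**Conclusion.** The concern holds in a limited form. The script asks for willingness as an eligibility item although it is not a criterion, very probably ends the call as ineligible on a No, and gives no way to record a refusal as such. Used before consent, it files burden refusals as ineligibility, and this can inflate the consent proportion by 1/(1 − w).

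The direction is certain if decliners are left out of the denominator. The size is unknown because the documents give neither the number declining nor the number eligible, and every percentage above is illustrative. The conclusion rests on three assumptions: that the blank after No is a stop, that the script comes before consent, and that the eligible count is taken from the script. If consent comes first, the rate is uninformative for a different reason. The conflict over order is therefore part of the same problem. The change is worth making, but it bears on how a feasibility rate is read and not on any treatment comparison.

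**What to change.** 1. Code a No at the willingness item as declined, eligible so far, with the reason, and keep it separate from ineligible. Alternatively, move the question to the consent discussion.
2. Define the denominator of the consent proportion in the SAP at one fixed time point: everyone who meets the criteria assessed up to then, decliners included.
3. Because some decliners would later fail the ISI or QDRS, report the rate with and without them.
4. Show refusals at the Appendix A interest question and at the Appendix B willingness item in the same screening flow.
5. Reconcile the order of consent and eligibility between the protocol's contact section, the appendices and the SAP. Reconcile also the workload callers are told about: 35 minutes weekly over six weeks in Appendix B, about an hour per session over six weeks in Appendix A, and a 9-week program in the intervention section.

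The cost is one new code, a short script edit and a few sentences in the SAP. The downside is that the reported consent rate becomes less favourable.

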**Are you currently participating in another research study?**

No (0)       Yes (1) If Yes, please describe: \_\_\_\_\_.

**Great, it looks like so far you are eligible to proceed – though we will need to do a few more tests to decide if you are eligible for the participation in the study. The next step is to conduct a screening for insomnia, and we will get back to you with your final eligibility.**

Subject's Initials

ID#

Date

Time

AM/PM

**Please answer the following questions as accurately as possible.**

## PITTSBURGH SLEEP QUALITY INDEX

**INSTRUCTIONS:**

The following questions relate to your usual sleep habits during the past month only. Your answers should indicate the most accurate reply for the majority of days and nights in the past month. Please answer all questions.

1. During the past month, what time have you usually gone to bed at night?

BED TIME \_\_\_\_\_

2. During the past month, how long (in minutes) has it usually taken you to fall asleep each night

NUMBER OF MINUTES \_\_\_\_\_

3. During the past month, what time have you usually gotten up in the morning?

GETTING UP TIME \_\_\_\_\_

4. During the past month, how many hours of actual sleep did you get at night? (This may be different than the number of hours you spent in bed.)

HOURS OF SLEEP PER NIGHT \_\_\_\_\_

***For each of the remaining questions, check the one best response. Please answer all questions.***

5. During the past month, how often have you had trouble sleeping because you . . .

- a) Cannot get to sleep within 30 minutes

Not during the last month _____	Less than once a week _____	Once or twice a week _____	Three or more times a week _____
---------------------------------	-----------------------------	----------------------------	----------------------------------

- b) Wake up in the middle of the night or early morning

Not during the last month _____	Less than once a week _____	Once or twice a week _____	Three or more times a week _____
---------------------------------	-----------------------------	----------------------------	----------------------------------

- c) Have to get up to use the bathroom

Not during the last month _____	Less than once a week _____	Once or twice a week _____	Three or more times a week _____
---------------------------------	-----------------------------	----------------------------	----------------------------------

d) Cannot breathe comfortably

Not during the last month \_\_\_\_\_ Less than once a week \_\_\_\_\_ Once or twice a week \_\_\_\_\_ Three or more times a week \_\_\_\_\_

e) Cough or snore loudly

Not during the last month \_\_\_\_\_ Less than once a week \_\_\_\_\_ Once or twice a week \_\_\_\_\_ Three or more times a week \_\_\_\_\_

f) Feel too hot

Less than

Three  
or  
more  
last

month \_\_\_\_\_ once a  
week \_\_\_\_\_ a week \_\_\_\_\_  
times a

Not during the

Once or  
twice

week \_\_\_\_\_

g) Had bad dreams

Less than

Three  
or  
more  
last

month \_\_\_\_\_ once a  
week \_\_\_\_\_ a week \_\_\_\_\_  
times a

Not during the

Once or  
twice

week \_\_\_\_\_

h) Have pain

Less than

Three  
or  
more  
last  
month

\_\_\_\_\_ once a week \_\_\_\_\_  
a week \_\_\_\_\_ times a  
week \_\_\_\_\_

Not during the

Once or  
twice

i) Other reason(s), please describe

---

---

How often during the past month have you had trouble sleeping because of this?

Not during the last month \_\_\_\_\_ Less than once a week \_\_\_\_\_ Once or twice a week \_\_\_\_\_ Three or more times a week \_\_\_\_\_

6. During the past month, how would you rate your sleep quality overall?

Very good \_\_\_\_\_

Fairly good \_\_\_\_\_

Fairly bad \_\_\_\_\_

Very bad \_\_\_\_\_

7. During the past month, how often have you taken medicine to help you sleep (prescribed or "over the counter")?

Not during the last month \_\_\_\_\_ Less than once a week \_\_\_\_\_ Once or twice a week \_\_\_\_\_ Three or more times a week \_\_\_\_\_

8. During the past month, how often have you had trouble staying awake while driving, eating meals, or engaging in social activity?

Not during the last month \_\_\_\_\_ Less than once a week \_\_\_\_\_ Once or twice a week \_\_\_\_\_ Three or more times a week \_\_\_\_\_

9. During the past month, how much of a problem has it been for you to keep up enough enthusiasm to get things done?

No problem at all \_\_\_\_\_

Only a very slight problem \_\_\_\_\_

Somewhat of a problem \_\_\_\_\_

A very big problem \_\_\_\_\_

10. Do you have a bed partner or roommate?

No bed partner or roommate \_\_\_\_\_

Partner/roommate in other room \_\_\_\_\_

Partner in same room, but not in same bed \_\_\_\_\_

Partner in same bed \_\_\_\_\_

If you have a roommate or bed partner, ask him/her how often in the past month you have had . .

a) Loud snoring

Not during the last month _____	Less than once a week _____	Once or twice a week _____	Three or more times a week _____
------------------------------------	--------------------------------	-------------------------------	-------------------------------------

b) Long pauses between breaths while asleep

Not during the Past month _____	Less than once a week _____	Once or twice a week _____	Three or more times a week _____
------------------------------------	--------------------------------	-------------------------------	-------------------------------------

c) Legs twitching or jerking while you sleep

Not during the Past month _____	Less than once a week _____	Once or twice a week _____	Three or more times a week _____
------------------------------------	--------------------------------	-------------------------------	-------------------------------------

d) Episodes of disorientation or confusion during sleep

Not during the Past month _____	Less than once a week _____	Once or twice a week _____	Three or more times a week _____
------------------------------------	--------------------------------	-------------------------------	-------------------------------------

e) Other restlessness while you sleep; please describe

---

Not during the last month _____	Less than once a week _____	Once or twice a week _____	Three or more times a week _____
------------------------------------	--------------------------------	-------------------------------	-------------------------------------

